4.1.1 Stratum A (Non-Malignant / Stem Cell Defects)

Day	Medication	Dose for <math>\geq 12</math> kg	Dose for <math>< 12</math> kg
Day -13	Alemtuzumab	Test Dose (1 mg)*, then 0.5 mg/kg (max 15 mg)	Test Dose (1 mg)*, then 0.5 mg/kg (max 6 mg)
Day -12	Alemtuzumab	0.5 mg/kg (max 15 mg)	0.5 mg/kg (max 6 mg)
Day -11	Alemtuzumab	0.5 mg/kg (max 15 mg)	0.5 mg/kg (max 6 mg)
Day -10	Busulfan	TBD by Wt-based formula 1 st dose at 9 pm	TBD by Wt-based formula 1 st dose at 9 pm
Day -9	Busulfan	TBD by PK (goal CSS = 600)	TBD by PK (goal CSS = 600)
Day -8	Busulfan	TBD by PK	TBD by PK
Day -7	Busulfan	TBD by PK	TBD by PK
Day -6	Busulfan	TBD by PK: Last dose at 3 pm (16 doses total)	TBD by PK: Last dose at 3 pm (16 doses total)
Day -5	Fludarabine Clofarabine	40 mg/m  10 mg/m 	1.33 mg/kg 0.33 mg/kg
Day -4	Fludarabine Clofarabine	40 mg/m  10 mg/m 	1.33 mg/kg 0.33 mg/kg
Day -3	Fludarabine Clofarabine	40 mg/m  10 mg/m 	1.33 mg/kg 0.33 mg/kg
Day -2	Fludarabine Clofarabine	40 mg/m  10 mg/m 	1.33 mg/kg 0.33 mg/kg
Day -1	Rest		
Day 0	Transplant	To begin $\geq 48$ hours from last dose of Flu and Clo	To begin $\geq 48$ hours from last dose of Flu and Clo

\* The test dose of Alemtuzumab (1 mg) will be given over 2 hours on the 1st day of conditioning. Four hours after the test dose, the first full dose of Alemtuzumab is given.

#### 4.1.2 Stratum B (Myeloid Malignancies) #

Day	Medication	Dose for <math>\geq 12</math> kg	Dose for <math><12</math> kg
Day -10	Busulfan	TBD by Wt-based formula 1 st dose at 9 pm	TBD by Wt-based formula 1 st dose at 9 pm
Day -9	Busulfan	TBD by PK (goal CSS = 900)	TBD by PK (goal CSS = 900)
Day -8	Busulfan	TBD by PK	TBD by PK
Day -7	Busulfan	TBD by PK	TBD by PK
Day -6	Busulfan	TBD by PK: Last dose at 3 pm (16 doses total)	TBD by PK: Last dose at 3 pm (16 doses total)
Day -5	Fludarabine Clofarabine	40 mg/m  10 mg/m 	1.33 mg/kg 0.33 mg/kg
Day -4	Fludarabine Clofarabine rATG ^	40 mg/m  10 mg/m  0.5 mg/kg	1.33 mg/kg 0.33 mg/kg 0.5 mg/kg
Day -3	Fludarabine Clofarabine rATG ^	40 mg/m  10 mg/m  2.5 mg/kg (1 mg/kg if UCB)	1.33 mg/kg 0.33 mg/kg 2.5 mg/kg (1 mg/kg if UCB)
Day -2	Fludarabine Clofarabine rATG ^	40 mg/m  10 mg/m  2.5 mg/kg (1 mg/kg if UCB)	1.33 mg/kg 0.33 mg/kg 2.5 mg/kg (1 mg/kg if UCB)
Day -1	rATG ^	2.5 mg/kg (1 mg/kg if UCB)	2.5 mg/kg (1 mg/kg if UCB)
Day 0	Transplant	To begin $\geq 48$ hours from last dose of Flu and Clo	To begin $\geq 48$ hours from last dose of Flu and Clo

# Because of limited data utilizing Alemtuzumab with Umbilical Cord Blood (UCB) Donors, this regimen will also be utilized for Stratum A Patients with UCB Donors (See Table 1), EXCEPT that their Busulfan goal CSS will still be 600.

^ Because of decreased GVL effect from matched related donors when using Bone Marrow or Umbilical Cord Blood as the stem cell source, only patients receiving Peripheral Blood Stem Cells from a matched related donor will receive rATG (See Table 1).

UCB recipients will receive “low dose” rATG (total dose of 3.5 mg/kg) based on recent data suggesting that “standard dose” rATG is associated with poor immunologic recovery.

#### 4.1.3 Supportive Care Practices:

- All UCSF Pediatric BMT Supportive Care Guidelines will be followed
- Premedications for Serotherapy (rATG and Alemtuzumab) will include: Acetaminophen (10 mg/kg), Diphenhydramine (1 mg/kg), and Dexamethasone (0.2 mg/kg).
- Appropriate Seizure prophylaxis will be administered prior to 1st dose of Busulfan and for at least 12 hours after the final dose.
- Fludarabine should be infused over 1 hour (9 am to 10 am) and Clofarabine should be infused over 2 hours immediately afterwards (10 am to 12 noon).

- e. To prevent hand-foot syndrome with Clofarabine, hydrocortisone (100 mg/m^2; 100 mg max dose) will be administered 1-2 hours prior to each dose unless Dexamethasone has been given within the last 24 hours.
- f. Ursodiol (6-7.5 mg/kg/dose twice daily) will be administered to all patients preferably 2 weeks prior to admission and no later than the day of admission. Ursodiol will continue until at least Day +30 or Day of Discharge, whichever is sooner, except for intolerance or side effects.
- g. Standard GVHD prophylaxis per the UCSF BMT Guidelines will be administered starting on Day -1. If a patient is unable to receive methotrexate on Day +1 due to liver enzyme elevations, mycophenolate mofetil should be substituted until the liver enzyme elevation has resolved and methotrexate can be re-initiated.
- h. Standard G-CSF administration will begin on Day +14, if needed.

#### 4.2 Study Tests:

##### 4.2.1 Standard of Care Testing:

Most tests performed on this trial will be done as standard of care for any patient undergoing allogeneic HCT. This will include:

- a. A minimum of twice weekly monitoring of CBC, chemistries, renal function, and liver enzymes during the first month post-HCT, and at least twice monthly for the first 100 days post-HCT.
- b. Engraftment studies by STR analysis of cell subsets beginning on ~Day +30 and then monthly until stable.

##### 4.2.2 Study Tests:

- a. To monitor for liver toxicity while receiving Clofarabine, daily liver enzymes (AST, ALT, Total and Direct Bilirubin, Alk Phos, and GGT) will be obtained starting on Day -5 and continuing until at least Day +6, at which point, the UCSF Pediatric BMT standard operating practices resume, which includes monitoring of liver enzymes twice weekly. Because daily tests of electrolytes are standard of care, this does not require any additional blood to be drawn.
- b. Patients will undergo pharmacokinetics (PK) to evaluate both Clofarabine and Fludarabine ("nucleoside analogue") exposure.

i. **Blood volume and weight:** In total, 11 blood samples will be collected over the entire course of nucleoside analogue treatment to evaluate drug exposure and pharmacogenomics. The total amount of blood volume needed for PK sampling is based on the weight of the child. For children weighing < 8 kg a total of 16 ml of blood will be drawn over a 4 day treatment course. For children weighing  $\geq$  than 8 kg, the amount of blood drawn over a 4 days treatment course will be a total of 24 ml.

ii. **DNA collection:** To assess the impact of genetic variants on nucleoside drug exposure a single blood collection for DNA and genotyping will occur on the day of admission prior to the start of chemotherapy. One (1 ml) of whole blood will be drawn into a 3 ml K2EDTA tube, placed on wet ice, and sent to the UCSF CTSI Core DNA Bank for immediate DNA isolation, quantification, and storage until analysis is performed.

iii. **PK sampling:** To evaluate plasma and intracellular drug concentrations blood samples will be obtained at 6 times over the course of

nucleoside treatment for a total 10 blood samples. Per protocol, Fludarabine will be administered intravenously over 60 minutes, followed by Clofarabine infusion over 2 hours. For convenience, blood collection times are based on the administration time of fludarabine. Plasma and intracellular drug concentrations are processed independently from one another and therefore require two different blood collection tubes at several of the PK sampling times.

iv. **Day 1 of nucleoside analogue therapy:** Following the administration of Fludarabine, 1ml of whole blood will be obtained at **2, 4, 8, and 24** hours after the start of infusion to evaluate **plasma** concentrations of both Clofarabine and Fludarabine. Blood samples for each plasma PK time point will be collected in a 2 mL spray dried K2EDTA tube and immediately place on wet ice. Within 60 minutes of collection all samples must centrifuged at 3400 rpm for 10 minutes at 4°C, the plasma removed, and stored at -70°C until analysis. PK sampling for the analysis of intracellular fludarabine drug levels will occur concurrently at **2** and **24** hours for correlation of plasma and intracellular drug concentrations. Blood samples for **intracellular** drug quantification will be collected in a 4 mL cell preparation tube with sodium citrate (BD Vacutainer ® CPT Tube) and processed for recovery of peripheral blood mononuclear cells. For children <8 kg only 2ml of blood will be collected for intracellular analysis.

v. **Day 2, 3, or 4 of nucleoside analogue therapy:** To evaluate drug accumulation over the course of treatment and assess inter-occasion variability, PK sampling will be repeated on Day 2, 3 or 4 of nucleoside analogue treatment. Blood samples will be collected at 2 and 24 hours following administration of fludarabine for a total of 4 blood samples. Blood samples for each **plasma** PK time point will be collected in a 2 mL spray dried K2EDTA tube and processed as previously described. As with Day 1 PK, blood collections for the analysis of intracellular nucleoside analogue drug concentrations will occur concurrently at **2** and **24** hours and processed for peripheral blood mononuclear cells.

vi. This PK sampling is identical to Study 10-00894 (Population Pharmacokinetics of Fludarabine in Pediatric Patients Undergoing Hematopoietic Cell Transplantation; [name], PI), thus patients will not need to co-enroll on that trial.

## 5.0 Statistics & Sample Size:

### 5.1 Primary Objective:

a. Severe Toxicity will be defined as death or Grade IV (by CTC AE 4.0) pulmonary or hepatic failure (including moderate veno-occlusive disease,aka VOD) related to the transplant conditioning regimen (as defined in Section 8.2) within 100 days post-HCT.

i. VOD will be defined by standard criteria. Patients must have Bilirubin >2.0 plus Hepatomegaly and/or RUQ pain plus Weight gain >5%.

b. The historic control will be the 37 patients detailed below, who have been treated with BU-FLU-Serotherapy based protocols at UCSF from 2000 – 2010 (and who would have fit the eligibility criteria for this trial). Of these 37 patients, 1 experienced TRM, but there were no cases of Grade IV pulmonary or hepatic failure, for a cumulative incidence of severe toxicity of 3% (90% upper confidence bound: 10%).

- c. Sample size justification is based on establishing that observed rates of toxicity with the addition of Clofarabine to a backbone of BU-FLU-Serotherapy are not worse than historical control levels. Since formal establishment of noninferiority is not possible given feasible sample sizes, expected toxicity rates are compared to historical rates in terms of the 90% exact binomial upper confidence bound for the observed proportion of events. For our planned sample size of 31, 3 or fewer events would lead to an upper bound within 10% of the corresponding upper bound for historical control levels. We consider a difference of 10% or smaller as evidence of similar levels of toxicity.
- d. If there are more than 3 events in the first 15 patients enrolled, the trial will be closed early for failing to achieve its safety goal.

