## 1.2 Specific Aims:

1.2.1 Primary Objective: To determine the toxicity of the addition of Clofarabine to a conditioning backbone of Busulfan plus Fludarabine in patients with myeloid malignancies and non-malignant diseases undergoing allogeneic HCT.

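### Section 5.1c reads a gap of at most 10 points between two upper bounds as similar toxicity, but its cut-off of 3/31 leaves an excess of about 16 points open and, on exact bounds, misses the 10-point limit

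*Combined protocol and SAP*

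**What the plan says.** The primary objective (section 1.2.1) is "To determine the toxicity of the addition of Clofarabine to a conditioning backbone of Busulfan plus Fludarabine". Section 5.1a defines severe toxicity as conditioning-related death or Grade IV pulmonary or hepatic failure, with moderate VOD included, by day 100. Section 5.1b gives the historical control as 1 event in 37 patients, reported as 3% with a 90% upper bound of 10%.

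Section 5.1c bases the sample size on showing that toxicity rates "are not worse than historical control levels". It concedes that "formal establishment of noninferiority is not possible given feasible sample sizes", so "expected toxicity rates are compared to historical rates in terms of the 90% exact binomial upper confidence bound". For 31 patients it states that "3 or fewer events would lead to an upper bound within 10% of the corresponding upper bound for historical control levels", and then gives the interpretation: "We consider a difference of 10% or smaller as evidence of similar levels of toxicity". Section 5.1d adds an early rule: "If there are more than 3 events in the first 15 patients enrolled, the trial will be closed early".

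Section 5.1 gives no interval for the difference between the two rates and no probability of meeting the criterion at any assumed true rate.

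**The concern.** There are two faults, and the first is the more important.

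**The quantity compared.** An upper bound is the observed rate plus an allowance for its own uncertainty. Subtracting the control's upper bound removes the control's allowance from the trial's, so uncertainty about the control counts in the new regimen's favour. A smaller control group with the same observed rate would have a higher bound and would make the criterion easier to meet. A limit on the excess must combine the two uncertainties, not offset them. Because the control is fixed at 1/37, the rule amounts to a cap of about 20% (10.11 + 10 = 20.11%) on the trial's own upper bound. That is not evidence of closeness to a control rate near 3%.

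**The cut-off.** Three events in 31 do not satisfy the 10-point limit on the exact bounds that the plan names.

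This is the only success criterion given for the primary objective, and the endpoint is death or life-threatening organ failure. With 3 events the report would call toxicity similar while an excess of about 16 points remained open. Whether exactly 3 of 31 meets the margin would depend on a rounding convention that the plan does not state.

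**Working it through.** **Inputs.** Control 1/37 = 2.70% (5.1b). Trial n = 31, cut-off 3 events, 3/31 = 9.68% (5.1c; total confirmed in 5.3a). Exact binomial bound at 90% and a margin of 10% (5.1c).

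**1. Reproduce the plan's control bound.** The one-sided 90% Clopper-Pearson upper bound is the p for which P(X ≤ x | n, p) = 0.10. For 1/37, (1 − p)^37 + 37p(1 − p)^36 = 0.10 gives p = 10.11%, which agrees with the stated 10%. The upper limit of a two-sided 90% interval would be 12.19%, which does not agree, so the plan uses the one-sided level. The 10% margin must mean percentage points: a relative 10% would cap the trial's bound at 10.11 × 1.1 = 11.1%, and even 1/31 exceeds that.

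**2. Apply the plan's rule, then compute the limit on the excess.** For the difference d = p1 − p2 (trial minus control), the Newcombe upper limit is d + √[(u1 − p1)² + (p2 − l2)²], where u1 and l2 are the Wilson upper limit for the trial and lower limit for the control, with z = 1.2816. At 3/31, u1 = 18.64% and l2 = 0.81%:

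6.97 + √[(18.64 − 9.68)² + (2.70 − 0.81)²] = 6.97 + 9.16 ≈ 16.1 points.

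| Events in 31 | Exact bound (%) | Gap to 10.11 (points) | Observed excess (points) | Newcombe limit (points) | Miettinen-Nurminen limit (points) | Newcombe limit minus gap |
|---|---|---|---|---|---|---|
| 0 | 7.16 | −2.95 | −2.70 | 2.67 | 2.46 | 5.62 |
| 1 | 11.98 | 1.87 | 0.52 | 7.74 | 7.87 | 5.87 |
| 2 | 16.27 | 6.16 | 3.75 | 12.09 | 12.29 | 5.93 |
| 3 | 20.30 | 10.19 | 6.97 | 16.14 | 16.37 | 5.95 |

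The gap is 5.6 to 6.0 points smaller than the limit on the excess at every count. Only 0 or 1 event keeps that limit at or below 10 points.

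**3. Sensitivity to method at 3/31.** The one-sided 90% limit on the excess is 14.6 (Wald), 15.6 (Agresti-Caffo), 16.1 (Newcombe), 16.4 (Miettinen-Nurminen) and 18.2 (Newcombe with continuity correction). The gap between bounds exceeds 10 points under every unrounded variant tried: Wilson 10.03, mid-P 10.07, Jeffreys 10.15, exact one-sided 90% 10.19, upper limits of two-sided 90% exact intervals 23.15 − 12.19 = 10.96, and one-sided 97.5% exact 11.59. Three events meet the margin only if both bounds are first rounded to whole percents (20 − 10 = 10).

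**4. Probability of passing, binomial, n = 31.**

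| True rate | P(≤ 3 events) | P(≤ 2 events) |
|---|---|---|
| 2.7% | 99% | 95% |
| 10% | 62% | 39% |
| 12.7% | 43% | 23% |
| 15% | 30% | 14% |
| 20% | 11% | 4% |

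The 12.7% row is 2.7 + 10, an illustrative yardstick that the plan does not set. Section 5.1d does not alter these figures, because 3 or fewer events in 31 implies 3 or fewer in the first 15.

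**5. Largest passing count if accrual falls short.**

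| n | Exact 10-point rule | Whole-percent rule | Cap of 20.3% on the trial's bound |
|---|---|---|---|
| 11–17 | 0 | 0 | 0 |
| 18–24 | 1 | 1 | 1 |
| 25–30 | 2 | 2 | 2 |
| 31 | 2 | 3 | 3 |

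**The case against.** The strongest reply is that the plan openly gives up formal noninferiority and offers a descriptive benchmark. It sets 10 points for the gap between bounds, not for a confidence limit on the difference, so holding it to the latter imposes a test it declined to run. This stands in part: failing a noninferiority test is not the charge. But the same item still treats the gap as evidence of similarity, and disclaiming the test does not make the gap measure what that wording implies.

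The wording about toxicity being no worse describes the aim of the sample-size justification and precedes the disclaimer. It is not a stated conclusion. That is fair. The similarity sentence is the inferential claim, although the aim should be reworded to match it.

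The margin miss is 0.19 point, disappears at the whole-percent precision the plan prints, and matters only at exactly 3 of 31, a count the plan names. That is also fair, so the miss is secondary. It still needs settling, because 3 of 31 is the boundary outcome and the plan names exact bounds but no rounding.

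Finally, the 16-point limit depends on the method, rests on one control event, and treats selected historical patients as a random sample. All five methods exceed 10 points, and a weak control is a reason to claim less. The pass probabilities assume 31 patients, and the stratum closing rules in 5.2.1d and 5.2.2d could reduce that number, so the table should be labelled accordingly.

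**Conclusion.** The concern holds and should be fixed. At the plan's own cut-off the data would not exclude an excess in severe toxicity of 16.1 points (one-sided 90%, Newcombe; 14.6 to 18.2 across methods), yet the result would be described as similar. On the exact bounds named in the plan, 3/31 gives a gap of 10.19 points and fails the 10-point limit; 2/31 gives 6.16 and meets it.

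The first result assumes independent binomial samples of 31 and 37 and takes the historical patients as comparable. The second needs only the one-sided 90% exact bound, which is the level that reproduces the plan's 10% for the control. The data would remain usable and the plan is candid about noninferiority. What has to change is the conclusion drawn from the criterion and the agreement between count and margin.

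**What to change.** Revise 5.1c as follows.

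- **Conclusion.** Drop the similarity wording and the not-worse aim. State the severe-toxicity rate excluded with one-sided 90% confidence (exact binomial) at the actual n. At n = 31 this excludes rates above 7.2% with 0 events, 12.0% with 1, 16.3% with 2 and 20.3% with 3.
- **Comparison.** Report the difference from 1/37 with its one-sided 90% upper limit and name the method, for example Newcombe.
- **Operating characteristics.** Print the pass probabilities from step 4 of the working, labelled as conditional on 31 patients.
- **Cut-off.** Choose one of two statements. Either the criterion is a trial upper bound of at most 20.3%, which keeps 3 of 31, or exact bounds govern the 10-point rule, which gives 2 of 31. The 20.3% figure is the bound at 3/31 and makes the existing whole-percent rule explicit. Strict arithmetic on the margin would give 20.11%. The cap changes no pass count under the whole-percent rule from n = 11 to 31, and the two options differ only at n = 31.

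The cost is a rewording of 5.1c, one interval and a short table, with no extra patients. The stated conclusion becomes less favourable. If exact bounds govern, the probability of passing at a true rate of 2.7% falls from 99% to 95%.

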## 5.2 Secondary Objectives:

### 5.2.1 Engraftment in patients with non-malignant diseases (Stratum A):

- a. Engraftment will be defined as the development of an ANC >500 for 3 consecutive days plus donor CD14/15 cells >70%.
- b. The historic control for Stratum A will be as follows:

Patients	# of High-Risk Patients	Engraftment	Overall Survival
Enrolled on BU-FLU-rATG 	5	2	4
Enrolled on BU-FLU-C 	5	2	2
Treated with BU off study (2005-10)	5	3	5
Summary	15	6	11

- c. Therefore, the engraftment rate in this population was only 40%. If the observed engraftment rate of this trial is as large as 83% (10/12), we would need a minimum of 12 patients in Stratum A to show a significant improvement ( $\alpha < 0.05$ ) in engraftment rate compared to historic controls at the 5% level.
- d. If 3 patients in Stratum A experience graft rejection, we will close this stratum early for failing to achieve superior engraftment compared to standard-of-care.

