### 5.2.2 Mixed-Chimerism in patients with high-risk myeloid malignancies (Stratum B):

- a. Full-donor chimerism will be defined by as  $\geq 99\%$  donor cells by STR analysis in all cell lines (CD3, CD14/15, and CD19) in peripheral blood.
- b. The historic control for Stratum B will be the 20 patients who were transplanted from 2005 – 2010 with BU-based regimens and who retrospectively would have been eligible for the current trial. Of these 20 patients, at 100 days post-HCT, only 8 (40%) patients had full-donor chimerism ([name], unpublished data).
- c. If the observed cumulative incidence of full-donor chimerism at Day 100 is at least 79%, we will need a minimum of 19 patients in Stratum B to show a

significant improvement (alpha < 0.05) in incidence of full donor chimerism compared to historic controls at the 5% level.

d. If 5 patients in Stratum B experienced mixed-donor chimerism at Day 100, we will close this stratum early for failing to achieve superior donor cell engraftment compared to standard-of-care.

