#### 5.3 Sample Size:

a. We will plan to accrue 12 patients to Stratum A and 19 patients to Stratum B, for a total of 31 patients.

b. Feasibility: From 2005 to 2010, we transplanted 15 patients that would have met the criteria for enrollment in Stratum A, and 22 patients that would have met the criteria for Stratum B. Presuming at least 90% participation of future patients, this trial should be able to accrue in approximately 6 years if referrals for transplant stay constant, or faster if they increase.

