### 9.1.3 Adverse Event Review and Monitoring

All grade(s) 3-5 adverse events, whether or not unexpected, and whether or not considered to be associated with the use of the study drug, will be entered into OnCore®, UCSF's Clinical Trial Management System.

All grade(s) 3-5 adverse events entered into OnCore® will be reviewed on a monthly basis at the Site Committee meetings. The Site Committee will review and discuss the selected toxicity, the toxicity grade, and the attribution of relationship of the adverse event to the administration of the study drug(s).

In addition, all adverse events or suspected adverse reactions considered “serious,” entered into OnCore® will be reviewed and monitored by the Data and Safety Monitoring Committee on an ongoing basis and discussed at DSMC meetings, which take place every six (6) weeks.

If a death occurs during the treatment phase of the study or within 30 days after the last administration of the study drug(s) and it is determined to be related either to the study drug(s) or to a study procedure, the Investigator or his/her designee must notify the DSMC Chair within **1 business day** of knowledge of the event. The contact may be by phone or e-mail.

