#### **9.1.4 Increase in Adverse Event Rates**

If an increase in the frequency of Grade 3 or 4 adverse events (above the rate reported in the Investigator Brochure or package insert) is noted in the study, a report should be submitted to the DSMC at the time the increased rate is identified. The report will indicate if the incidence of AEs observed in the study is within the range stated in the Investigator Brochure or package insert.

If at any time the Investigator stops enrollment or stops the study due to safety issues the DSMC Chair and administrator must be notified within **1 business day** via e-mail. The DSMC must receive a formal letter within **10 business days** and the CHR must be notified.

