Myeloablative HCT in general, whether done as part of a clinical trial or as a standard-of-care treatment, is an inherently risky procedure, with a known risk of TRM and many non-fatal toxicities, independent of the potential addition of novel agent(s). Given that only patients at high risk of graft rejection or relapse (frequently fatal events) are eligible for this trial, only a significant increase in TRM or very severe (Grade IV hepatic or pulmonary) toxicities would be sufficient cause to suspend further development of Clofarabine to potentially improve overall outcomes following HCT.

**9.3. Safety Monitoring Plan:** Subjects will remain in the hospital for at least 3 weeks following administration of the study medication Clofarabine. This will allow sufficient time to monitor for the development of severe adverse events potentially attributable to Clofarabine. During this time, as part of routine post-HCT standard of care, patients will have daily physical exams, frequent vital sign monitoring, and laboratory testing at least twice weekly (and daily during the initial period). The safety laboratory studies (i.e. hepatic transaminases) will be reviewed on a continuous basis by the investigators. Following discharge from the hospital and until Day +100, patients will be followed closely in clinic at least twice monthly, with laboratory studies done at least once weekly, all per the UCSF Pediatric BMT SOP. Patients will also have a contact number to report any potential adverse events that occur in between scheduled clinic visits. Should a serious adverse event occur during the course of the study, it will be reported immediately to the Committee on Human Research (Institutional Review Board) at the University of California San Francisco (UCSF) in accordance with current University guidelines for reporting possible adverse events.

**9.3.1 Frequency of Safety Reviews:** Safety monitoring will be conducted monthly on each patient.

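### The toxicity closure rule stops applying after patient 15, so a fourth severe event in patients 16–31 fails the safety criterion without requiring closure

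*Combined protocol and SAP*

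**What the plan says.** Severe toxicity (5.1.a) is death, Grade IV pulmonary or hepatic failure, or moderate VOD related to conditioning, within 100 days of transplant. The historic control (5.1.b) had 1 such event in 37 patients: 3%, with a 90% upper bound of 10%.

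Section 5.1.c sets the benchmark: "For our planned sample size of 31, 3 or fewer events would lead to an upper bound within 10" percent of the control's upper bound. A gap of that size or less is read as similar toxicity.

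Section 5.1.d gives the closure rule: "If there are more than 3 events in the first 15 patients enrolled, the trial will be closed early". The stated reason is that the safety goal has not been met.

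The stratum rules have no patient-number limit. In 5.2.1.d: "If 3 patients in Stratum A experience graft rejection, we will close this stratum early". In 5.2.2.d: "If 5 patients in Stratum B experienced mixed-donor chimerism at Day 100, we will close this stratum early".

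Other oversight carries no event count. Serious events are "discussed at DSMC meetings, which take place every six (6) weeks" (9.1.3). Section 9.1.4 sets out who must be told "If at any time the Investigator stops enrollment or stops the study due to safety issues", but not when to stop. Section 9.2.1 says that "only a significant increase in TRM or very severe (Grade IV hepatic or pulmonary) toxicities would be sufficient cause to suspend further development" of the drug, without a number or a time point.

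**The concern.** Sections 5.1.c and 5.1.d use the same limit, 3 events, but 5.1.d enforces it only up to patient 15. An event count cannot fall. Once a fourth event occurs, at whatever patient number, 3 or fewer in 31 is out of reach. If that happens at patient 16 or later, the plan's safety criterion has failed, and whether more patients receive the regimen is left to judgment.

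The events are death, life-threatening lung or liver failure and VOD. The plan gives no reason for dropping the limit at patient 16, and does not say that enrolment should continue after a failed criterion to sharpen the toxicity estimate. The efficacy rules for the two strata run throughout accrual; the rule for the primary safety endpoint does not.

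**Working it through.** **Inputs.** Control 1/37; planned size 31 (12 in Stratum A, 19 in Stratum B); limit 3 events; early window 15 patients; stratum closure at 3 failures (A) and 5 failures (B); accrual of about 6 years (5.3.b: "this trial should be able to accrue in approximately 6 years"). The true toxicity rates p are assumptions.

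**1. The plan's own figures.** The one-sided exact 90% upper bound for x events in n is the 0.90 quantile of Beta(x+1, n−x).

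| Events | Upper bound | Points above control |
|---|---|---|
| 1/37 (control) | 10.1% (plan prints 10%) | – |
| 2/31 | 16.3% | 6.2 |
| 3/31 | 20.3% | 10.2 |
| 4/31 | 24.1% | 14.0 |

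The printed 10% is reproduced. Three events meet the 10-point margin only after rounding; four clearly do not, and four events in fewer than 31 patients give a higher bound still.

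**2. How often the fourth event comes early or late, if accrual otherwise runs to 31.** Early = P(Bin(15,p) ≥ 4). Late = P(Bin(31,p) ≥ 4) − early.

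| True rate p | Early: 5.1.d closes | Late: no rule applies | Fourth event at any time |
|---|---|---|---|
| 3% | 0.1% | 1.3% | 1.3% |
| 5% | 0.5% | 6.2% | 6.7% |
| 10% | 5.6% | 32.1% | 37.6% |
| 15% | 17.7% | 52.7% | 70.4% |
| 20% | 35.2% | 54.1% | 89.3% |
| 25% | 53.9% | 43.1% | 96.9% |
| 30% | 70.3% | 29.0% | 99.3% |

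Rows may differ from their sums by 0.1 through rounding. Early and late are equal at p = 23.3%. Below that rate 5.1.d misses more failures than it catches; above it, the reverse.

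**3. With the stratum rules included.** Step 2 is an upper limit, because a stratum may close first for efficacy. Simulation (200,000 trials per scenario): 12 A and 19 B patients in random order, A closing at 3 failures and B at 5, toxicity independent of engraftment, outcomes known at once. At target efficacy (failure rates 2/12 and 4/19), the stratum rules alone close A in 32% and B in 37% of trials.

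| p | Early | Late | Further patients after a late event | Enrolled as written | Enrolled if closed at fourth event |
|---|---|---|---|---|---|
| 10% | 5.5% | 26.4% | 6.0 | 27.6 | 26.0 |
| 15% | 17.7% | 44.9% | 6.9 | 25.5 | 22.4 |
| 20% | 35.2% | 48.2% | 7.7 | 22.5 | 18.7 |
| 25% | 54.0% | 39.7% | 8.5 | 19.0 | 15.6 |
| 30% | 70.3% | 27.5% | 9.3 | 15.8 | 13.2 |

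The average saving per trial is the chance of a late event times the further patients:

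- 10%: 0.264 × 6.0 = 1.6
- 20%: 0.482 × 7.7 = 3.7
- 30%: 0.275 × 9.3 = 2.6

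At 3% and 5% it is about 0.05 and 0.26 patients.

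**4. Worse efficacy, toxicity 20%.** With 40% failure in both strata (assumption): late 21%, 3.9 further patients, enrolment 16.6 as written against 15.8. With the historic 60% failure: late 3%, 1.6 further patients, a saving of about 0.04.

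**5. Reporting lag.** 31 patients over 6 × 365 = 2,190 days is 1.4 patients per 100 days. At p = 20% and target efficacy, a lag of 1 or 2 patients cuts the saving from 3.7 to 3.4 or 3.1.

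**The case against.** A single early look followed by a final benchmark is a recognised design. Section 5.1.c is worded as a sample-size justification and disclaims a formal noninferiority test, so missing it does not logically oblige closure. The primary objective is to determine toxicity, and later patients still contribute to that. Late events are also watched: the Site Committee reviews Grade 3–5 events (weekly in 8.4, monthly in 9.1.3), the DSMC meets every six weeks, related deaths during treatment or within 30 days of study drug are reported to its chair within one business day, and slow accrual leaves time to act. Section 9.2.1 sets a high bar for suspending development because rejection and relapse are themselves often fatal. Finally, the largest saving needs a true rate of 20%, twice the historic upper bound, together with good efficacy.

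Much of this stands. It is a gap in the written rule and not an arithmetic error, nobody is barred from stopping the trial, and the benefit depends on rates the documents do not give. The simulation also treats toxicity as independent of engraftment, although a death before Day 100 can preclude the chimerism assessment. The stratum rules are efficacy rules, so they show only that the plan uses cumulative limits elsewhere.

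It does not remove the point. Section 5.1.d itself equates more than 3 events with missing the safety goal, and nothing in the plan explains why the same count ceases to matter at patient 16. The remaining safeguards have no event threshold.

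**Conclusion.** The concern holds; it should be fixed. After a fourth event in patients 16–31 the 5.1.c criterion is unattainable and no written rule requires closure. If accrual otherwise runs to 31, this happens in 32% of trials at an assumed true rate of 10% and in 54% at 20%; 5.1.d catches only 5.6/37.6 = 15% and 35.2/89.3 = 39% of the trials that breach the limit.

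In patients, the effect is moderate. At target efficacy the average saving is 1.6 to 3.7 patients for true rates between 10% and 30%. It is negligible at rates near the control's 3%, and also at 20% toxicity when efficacy is at historic levels. These figures assume independent patients and, except for the lag check, immediate outcomes.

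**What to change.** Replace 5.1.d with a cumulative limit, for example: *If more than 3 severe-toxicity events occur at any point up to patient 31, enrolment to both strata will close for failing to achieve the safety goal.* State the limit as a number and do not define it by reference to the 10-point margin, because 3/31 exceeds that margin slightly before rounding (10.2 points). If the sponsor does intend a single early look, 5.1.d should say so, give the reason, and state what happens after a late fourth event.

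The change is one sentence in an amendment; the case report form already records these events through Day +100. Two costs should be stated with it:

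- Secondary and PK data may be cut short.
- Closure becomes more likely at rates compatible with the control data. If accrual otherwise runs to 31, it rises from 0.1% to 1.3% at a true rate of 3%, from 0.5% to 6.7% at 5%, and from 5.6% to 37.6% at 10%. With the stratum rules at target efficacy, the new figures are 1.1%, 5.3% and 31.8%.

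Every added closure is a trial that would have failed 5.1.c anyway.
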